In an effort to decrease pain control, it is common practice for local anesthetics to be infiltrated into the surgical wound. Individual studies have shown that infiltrations with bupivacaine specifically have decreased intraoperative and postoperative narcotic use, decreased pain scores in the immediate postoperative period²⁴⁻²⁶. However, upon meta-analysis of randomized clinical trials studying the effect of wound infiltration with bupivacaine or ropivacaine it was found that postoperative pain severity was only decreased at 2 hours postoperatively and postoperative analgesic consumption did not change²⁷. In light of this, there continues to be a need for improvement in postoperative pain management for mastectomy and subsequent breast reconstruction.

One such medication which has been suggested for improvement in pain control after mastectomy and breast reconstruction is Exparel (Pacira Pharmaceuticals, Inc., San Diego, CA). It is a relatively recent bupivacaine multi-vesicular liposomal delivery system that allows slow release of bupivacaine, resulting in local anesthetic effects for up to 72-96 hours after injection. It is a safe pain control modality with a similar side effects profile to bupivacaine HCL and does not compromise breast implant integrity¹³⁻¹⁴.

Side effects of Exparel primarily includes GI upset (nausea and vomiting) which can occur in greater than 10% of patients. More rare side effects include hypotension (2-10%), insomnia (2-10%), pruritus (3%), postoperative anemia (2-10%), and muscle spasm (2-10%). Similar to other local anesthetics, dose related toxicity can occur and can lead to central nervous system excitation or depression. Exparel has a half-life of 24-34 hours and is hepatically metabolized and renally excreted. It should be used in caution with patients with moderate-severe hepatic or renal impairment because of the increased risk of toxicity. Exparel may increase the toxicity of lidocaine and bupivacaine. Bupivacaine can be administered with or immediately before Exparel as long as the milligram dose ratio of bupivacaine to Exparel is not greater than 1:2. Furthermore, Exparel may increase the effect of neuromuscular blocking agents. Exparel is not recommended in pregnant patients as there have been no studies conducted in this population and high doses used in animal models have been shown to decrease fetal

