2.2 Secondary Objective(s)

- 2.2.1 To evaluate the effect of liposomal bupivacaine on cumulative pain control within the first 48 hours after mastectomy and breast reconstruction
- 2.2.2 To evaluate the effect of liposomal bupivacaine on the amount of postoperative narcotic use after mastectomy and breast reconstruction for the first month after surgery
- 2.2.3 To evaluate the effect of liposomal bupivacaine on length of hospital stay after mastectomy and breast reconstruction
- 2.2.4 To evaluate the effect of liposomal bupivacaine on hospital readmission rates a within 2 months after mastectomy and breast reconstruction
- 2.2.5 To evaluate the effect of liposomal bupivacaine on the occurrence of opioid adverse effects within the first week of surgery after mastectomy and breast reconstruction
- 2.2.6 To evaluate the effect of liposomal bupivacaine on the trajectory of postoperative pain control within 2 months after mastectomy and breast reconstruction

THE USE OF LIPOSOMAL BUPIVACAINE FOR PAIN CONTROL FOLLOWING
MASTECTOMY AND IMMEDIATE IMPLANT BASED BREAST RECONSTRUCTION

Wake Forest Baptist Comprehensive Cancer Center
CCCWU # 99517

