5.0 Study Outcomes and Study Measures

5.1 Primary Outcome

5.1.1 The primary outcome of this study is the mean visual analog scores (scale of 0-10) within the first 48 hours postoperatively. This will be measured every 12 hours for the first 48 hours and will be assessed by the level of breast pain associated with arm movements while eating.

5.1.1.1 Visual analog scores in mastectomy patients with oral and IV narcotics are approximately 5.0 at 24 hours and 4.8 at 48 hours¹⁷

5.1.1.2 For patients with local infiltration of Liposomal bupivacaine after implant based reconstruction, visual analog scores at 24hrs were 3.8 on average¹⁸

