The study will be double blinded to both patients and providers including plastic and general surgeons involved in their operative care. We will enroll our patients in pharmacy randomization program, in which the pharmacy will deliver the appropriate medication per assigned group.

To monitor our primary outcomes, patients will be asked to rate their pain level on a visual analog scale (Table 2, Appendix Z) with activity every 12-hours after surgery during their post-procedure stay. The activity for which they will rate their pain will be the arm movements associated with eating. In the hospital, their visual analog scores will be provided to each patient in person by their nurse every 12 hours. Subject's pain scores will continue to be recorded every 12 hours via a phone call from a study team member for the first 48 hours after discharge. Additionally, while in the hospital, the amount of narcotics used will be recorded and converted into morphine equivalents.

Upon discharge, patients will be given a sheet to record their pain level and the amount of narcotics & benzodiazepines used (Appendix K). Both the amount of narcotics & benzodiazepines and the pain level are to be reported at the time of taking any narcotics & benzodiazepines. Patients will follow up with our clinic at 1 week, 3 weeks, and 5 weeks postoperatively. At week 1 patients will bring in their medication and pain diary, and fill out a pain assessment (Appendix G) in addition to a questionnaire assessing breast cancer surgery

THE USE OF LIPOSOMAL BUPIVACAINE FOR PAIN CONTROL FOLLOWING MASTECTOMY AND IMMEDIATE IMPLANT BASED BREAST RECONSTRUCTION

Wake Forest Baptist Comprehensive Cancer Center
CCCWU # 99517

disability (Appendix H)²³. During subsequent appointments made at 3 and 5 weeks postoperatively, they will be assessed and receive the pain assessment and breast cancer surgery disability assessments as well. When tissue expansion is initiated will be determined by the primary surgeon, but we will track the dates of the initiation of expansion as this will impact pain scores within the electronic medical record.

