6.4 Duration of Follow Up

Patients will be seen at one week, three weeks and five weeks postoperatively at which time they will receive pain and disability assessments.

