rate, 2-sided alpha of 0.05 and 80% power, we could detect a difference of 31% between the 2 arms using a Fisher's Exact Test

- 10.2.6 For trajectory of postoperative recovery from pain, Growth curve analysis of pain intensity with movement scores over the first two months, using an initial log (time) model and a Bayesian change point analysis
 - 10.2.6.1 Groups will be compared for intercept and slope of the trajectory of pain intensity up to the first change point
 - 10.2.6.2 For the entire population, the impact of the optimism-catastrophizing continuum and other predictive factors for intercept and slope will be explored

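### The arms' pain trajectories are compared only up to an estimated first change point, so no arm comparison of later pain is specified although the objective covers two months

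*Combined protocol and SAP*

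**What the plan says.** Objective 2.2.6 asks for the effect of liposomal bupivacaine "on the trajectory of postoperative pain control within 2 months after mastectomy and breast reconstruction". Section 10.2.6 models movement-pain scores over that period "using an initial log (time) model and a Bayesian change point analysis". Section 10.2.6.1, with the same wording in 5.2.6.2, then gives the arm comparison: "Groups will be compared for intercept and slope of the trajectory of pain intensity up to the first change point". The item that follows concerns the whole study population, not the arms.

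The plan does not say whether the change point is common, per arm or per patient, what happens if none is found, or where time zero lies for the intercept.

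The scores come in two blocks. In hospital they are taken every 12 hours. After discharge, under Section 6.1, "pain scores will continue to be recorded every 12 hours via a phone call from a study team member for the first 48 hours". Later scores come from clinic (Section 6.4): "Patients will be seen at one week, three weeks and five weeks postoperatively". Section 1.0 describes the study drug as "resulting in local anesthetic effects for up to 72-96 hours after injection".

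**The concern.** The end of the comparison window is itself an outcome. It is estimated from the pain scores, and a drug that acts for three to four days could put a bend in one arm's curve that the other lacks. By-arm fitting could then compare slopes over different periods. Common fitting leaves everything after the bend without a stated arm comparison, and the week 1, 3 and 5 pain scores have no other between-arm analysis in the plan.

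The second issue is how the two parameters would be read. An arm that starts lower and later meets the other arm has a flatter slope by construction. The report could then show a better intercept and a worse slope, with no rule for reading them together and no direct answer about pain in the later weeks.

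**Working it through.** The plan gives no power, effect size or alpha for this outcome, so there is no figure to reproduce. Two checks follow.

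**1. Which visits the window can leave out.** Section 5.2.3.1 cites an average stay of 41 to 47 hours, and calls run for 48 hours after discharge: 41 + 48 = 89 h and 47 + 48 = 95 h. With the 36-hour stay expected in 5.2.3.2 the last call is at 36 + 48 = 84 h. The frequent scores therefore end at about the time the drug effect does (72 to 96 h). Only weeks 1, 3 and 5 (168, 504 and 840 h) remain. A common change point at or before the last call leaves all three visits outside the comparison; one at week 1 leaves out two. When a 1-point arm difference confined to weeks 1 to 5 was simulated, the slope test in the common window stayed close to chance level.

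**2. What the slope does when early benefit fades.**

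Inputs from the documents:
- Pain on oral and IV narcotics "approximately 5.0 at 24 hours and 4.8 at 48 hours" (5.1.1.1), and 3.8 at 24 h with liposomal bupivacaine (5.1.1.2): a difference of 5.0 − 3.8 = 1.2.
- Wear-off at 72 or 96 h (1.0); 25 per arm (10.3).

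Assumed:
- Control falls linearly in ln(time) to 2 at five weeks. The range tried is 1 to 3.97; 3.97 extends the cited fall: (4.8 − 5.0)/ln 2 = −0.29 per ln hour, and 5.0 − 0.29 × ln 35 = 5.0 − 0.29 × 3.555 = 3.97.
- The 1.2 benefit holds to 48 h, fades linearly in ln(time) to zero at wear-off, and the arms are equal afterwards.
- Scores every 12 h to 96 h, then weeks 1, 3 and 5. Between-patient SD 1.5, within-patient SD 1.2.

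Curves, with wear-off at 96 h:
- Control: C(t) = 5.0 − (3.0/3.555) × ln(t/24), so the slope is −0.84 throughout.
- Liposomal: C(t) − 1.2 up to 48 h; C(t) − 1.2 × ln(96/t)/ln 2 from 48 to 96 h; C(t) after that. It is never above control. Its slope is −0.84 before 48 h and −0.84 + 1.2/0.693 = +0.89 between 48 and 96 h.

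The slopes are least-squares fits on ln(t/24). The last column is from 1,000 simulated trials, comparing per-patient slopes by t-test.

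| Window ends | Control slope | Liposomal slope | Fitted 24 h value, control v liposomal | Liposomal slope significantly shallower |
|---|---|---|---|---|
| 48 h | −0.84 | −0.84 | 5.00 v 3.80 | 3% |
| 72 h | −0.84 | −0.53 | 5.00 v 3.86 | not run |
| 96 h | −0.84 | −0.28 | 5.00 v 3.85 | 87% |
| 168 h | −0.84 | −0.27 | 5.00 v 3.85 | 96% |
| 840 h (all) | −0.84 | −0.47 | 5.00 v 3.96 | 99% |
| Estimated, common | −0.84 | −0.40 (mean) | – | 74% |
| Estimated, by arm | −0.84 | −0.33 (mean) | – | 65% |

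The estimated change points use a least-squares broken stick as a stand-in for the Bayesian fit. By arm, the median change point was 72 h (control) and 168 h (liposomal). Across the full range of five-week pain and both wear-off times, a 96 h window gives control slopes of −1.13 to −0.29 and liposomal slopes of −0.56 to +0.40.

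A second set of assumed curves, with the same SDs, gave the same picture. Control was 5.0, 4.8 and 4.6 at 24, 48 and 84 h, then 4.0, 2.0 and 1.2 at weeks 1, 3 and 5. The liposomal arm was 1.2 lower at 24 h, 0.8 lower at 48 h, and equal from 84 h. The liposomal slope was significantly shallower in 86 to 89% of runs with a common change point and in 97% over all five weeks. If the 1.2-point benefit was made to persist, the figure fell to 4%, which is chance.

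**The case against.** **The cut-off does not cause the flatter slope.** This stands. Convergence after a lower start causes it, and the table shows it at least as strongly with no cut-off. A longer or fixed window would not cure a slope contrast.

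**The intercept is compared too.** This also stands. A lower start with a flatter slope is a coherent description of early benefit followed by convergence. Early pain is tested separately through the 48-hour score and the 48-hour area under the curve, and narcotic use over the first month. A reader might infer that the plan will score effective early analgesia as slower recovery, or the drug as worse overall. The documents do not support that: the reversal needs a window that reaches into wear-off and pain that catches up.

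**Later weeks may be compared after all.** Partly right. A reader might infer that they never are. A late or absent change point would bring later visits into the window, and the common change point often fell at week 1 in the simulation. What stands is that no comparison of pain after the change point is specified.

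**Different change points by arm need not reflect the drug.** Correct. They differed in more than half of simulated trials even with no treatment effect. That makes by-arm windows unstable rather than proving that treatment moves them.

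**The 1.2 is not a contrast of this trial's arms.** Correct. The 5.0 comes from patients on narcotics; the comparator here is bupivacaine infiltration. The only cited liposomal-versus-bupivacaine pain figures are 72-hour areas of 441 and 461. If these are in point-hours (an assumption), the gap is 20/72 = 0.28 points, and the second set of curves then gives a significantly shallower slope in only 8 to 10% of runs. The plan's own target of 115 units would be 115/72 = 1.6 points, so the size is genuinely uncertain.

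**Conclusion.** The concern holds in a limited form. The one stated arm comparison of the trajectory stops at a point estimated from post-randomisation scores, and nothing is specified beyond it, while the objective runs to two months. This follows from the text and needs no simulation. An arm difference at the later visits can be missed.

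That slope and intercept may point in opposite directions is a conditional addition. It depends on convergence with control. The illustrative rate runs from chance (benefit persists, or the window closes by 48 h) to 65–74% with an estimated change point under the first set of curves and 86–89% under the second. Those percentages rest on assumed later pain levels, assumed SDs, a 1.2-point difference borrowed from different populations, and a least-squares stand-in for the Bayesian fit. They should not be quoted as the trial's expected error rate.

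This affects one secondary outcome and leaves the primary analysis untouched. The change is a worthwhile, inexpensive improvement.

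**What to change.** In 5.2.6.2 and 10.2.6.1, base the arm comparison on a mixed model of all scheduled movement-pain scores. Time should be time since surgery, with analysis times fixed in advance and common to both arms. Report the arm difference in estimated mean pain, with confidence intervals, at pre-set times through week 5 (for example 24, 48 and 84 h and days 7, 21 and 35). Give one joint test that covers the arm main effect and the arm-by-time interaction together; a test of the interaction alone would miss a constant difference. Keep the change-point intercept and slope as a descriptive analysis, and state whether the change point is common or by arm and what is reported if none is found. Settle this before unblinded data are seen.

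The cost is a change of wording in two places, with no new data. The downside is several fixed-time differences instead of two parameters, and a joint test that is less sensitive to a constant shift than a single contrast would be.

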10.3 Power and Sample Size

We will have a power of 80%, as described in 10.1.1, with a sample size of 25 patients in each arm for a total of 50 patients

10.4 Accrual Rate

We plan on accruing 25 new patients per year until the goal of 50 total patients is reached.

10.5 Estimated Study Length

Estimated study length will be approximately 2 years. This will include patient enrollment through the 5 week patient follow up period.

10.6 Interim Analysis Plan

We will plan on performing an interim analysis for the primary outcome and secondary outcomes after there are at least 10 patients in each treatment group in order to detect the evidence of severe side effects in either group. We will perform a secondary analysis after there are at least 20 patients in each group to monitor for more rare side effects including but not limited to bradycardia, tachycardia, respiratory distress, hypotension or neurological depression.

THE USE OF LIPOSOMAL BUPIVACAINE FOR PAIN CONTROL FOLLOWING
MASTECTOMY AND IMMEDIATE IMPLANT BASED BREAST RECONSTRUCTION

Wake Forest Baptist Comprehensive Cancer Center
CCCWU # 99517

References

4. Shwkhawat L, Busheri L, Dixit S, Patel C, Dhar U, Koppiker C. Patient-Reported Outcomes Following Breast Reconstruction Surgery and Therapeutic Mammoplasty: Prospective Evaluation 1 year Post-Surgery with Breast-Q Questionnaire. *Indian J Surg Oncol.* Dec 2-15. 6(4): 356-62.
6. Morrison JE Jr, Jacobs VR. Reduction or elimination of postoperative pain medication after mastectomy through use of a temporarily placed local anesthetic pump vs. control. *Zentralbl Gynakol.* Jan 2003. 125(1): 17-22.
9. Strang P. Cancer pain- a provoker of emotional, social and existential distress. *Acta Oncol.* 1998. 37(7-8): 641-4.

Appendix A – Eligibility Checklist

IRB Protocol No. _____	WFBCCC Protocol No. _____
Study Title: THE USE OF LIPOSOMAL BUPIVACAINE FOR PAIN CONTROL FOLLOWING MASTECTOMY AND BREAST RECONSTRUCTION	
Principal Investigator: [name]., Ph.D.	

Inclusion Criteria (as outlined in study protocol)	Criteria is met	Criteria is NOT met	Source Used to Confirm * (Please document dates and lab results)
All patients who receive a bilateral mastectomy with immediate implant based breast reconstruction			
Age >18 years			
Ability to understand and willingness to sign IRB-approved informed consent document			
Patients who will receive a tissue expander or a direct permeant implant for breast reconstruction			
ASA patient status I-III			
Patients having sub-pectoral implant placement			
Exclusion Criteria (as outlined in study protocol)	Criteria NOT present	Criteria is present	Source Used to Confirm * (Please document dates and lab results)
Patients who receive an autologous tissue reconstruction			
Patients who receive a unilateral reconstruction			
Patients who weigh < 50 kg			
Patients who will undergo axillary lymph node dissection			
Patients who abuse narcotics or have chronic pain (using greater than 40 mg equivalents of oxycodone per day)			
Patients who are wards of the state			
History of allergic reactions attributed to compounds of similar chemical or biologic composition to bupivacaine or liposomal bupivacaine.			
Patients having pre-pectoral implant placement			

THE USE OF LIPOSOMAL BUPIVACAINE FOR PAIN CONTROL FOLLOWING
MASTECTOMY AND IMMEDIATE IMPLANT BASED BREAST RECONSTRUCTION

Wake Forest Baptist Comprehensive Cancer Center
CCCWU # 99517

Pregnant women are excluded from this study because liposomal bupivacaine is a/an class C agent with the potential for teratogenic or abortifacient effects. Because there is an unknown but potential risk for adverse events in nursing infants secondary to treatment of the mother with liposomal bupivacaine, breastfeeding should be discontinued if the mother is treated with liposomal bupivacaine.			
--	--------------------------	--------------------------	--

This subject is eligible / ineligible for participation in this study.

ORIS Assigned PID: _____

Signature of research professional confirming eligibility: _____

Date: ____ / ____ / ____

Signature of Treating Physician: _____

Date: ____ / ____ / ____

Signature of Principal Investigator**: _____

Date: ____ / ____ / ____

* Examples of source documents include clinic note, pathology report, laboratory results, etc. When listing the source, specifically state which document in the medical record was used to assess eligibility. Also include the date on the document. Example: "Pathology report, 01/01/14" or "Clinic note, 01/01/14"

**Principal Investigator signature can be obtained following registration if needed

**THE USE OF LIPOSOMAL BUPIVACAINE FOR PAIN CONTROL FOLLOWING
MASTECTOMY AND IMMEDIATE IMPLANT BASED BREAST RECONSTRUCTION**

Wake Forest Baptist Comprehensive Cancer Center
CCCFU # 99517

Appendix B – Protocol Registration Form

DEMOGRAPHICS

Patient: Last Name: _____ First Name: _____

MRN: _____ DOB (mm/dd/yy): ____ / ____ / ____

ZIPCODE: _____

SEX: Male Female

Ethnicity (choose one): Hispanic

Non-Hispanic

Race (choose all that apply): WHITE BLACK ASIAN

PACIFIC ISLANDER NATIVE AMERICAN

Height: _____.____ inches Weight: _____.____ lbs. (actual)

Surface Area: _____.____ m²

Primary Diagnosis: _____

Date of Diagnosis: ____ / ____ / ____

Performance Status: ____ ECOG Karnofsky

PROTOCOL INFORMATION

Date of Registration: _____ / _____ / _____

MD Name (last): _____

Date protocol treatment started: _____ / _____ / _____

Informed written consent: YES NO

(consent must be signed prior to registration)

Date Consent Signed: _____ / _____ / _____

PID # (to be assigned by ORIS): _____

Protocol Registrar can be contact by calling [contact] between 8:30 AM and 4:00 PM, Monday – Friday.

Completed Eligibility Checklist and Protocol Registration Form must be hand delivered, faxed or e-mailed to the registrar at [name] or [contact].

THE USE OF LIPOSOMAL BUPIVACAINE FOR PAIN CONTROL FOLLOWING
MASTECTOMY AND IMMEDIATE IMPLANT BASED BREAST RECONSTRUCTION

Wake Forest Baptist Comprehensive Cancer Center
CCCFU # 99517

Appendix C - Race & Ethnicity Verification Form

Thank you so much for helping us to verify your race and ethnicity to ensure the quality of our information. As a brief reminder, the information you provide today will be kept confidential.

1. Are you:
 Hispanic or Latino/a
 Not Hispanic or Latino/a
2. What is your race? One or more categories may be selected.
 White or Caucasian
 Black or African American
 American Indian or Alaskan Native
 Asian
 Native Hawaiian or Other Pacific Islander
 Other, Please Specify: _____

Internal use only:

Name: _____ MRN#: _____

Was the self-reported race and ethnicity of the participant verified at the time of consent?

Yes No

Was a discrepancy found? Yes No

If yes, please provide what is currently indicated in the EMR:

Ethnicity: _____ Race: _____

Additional comments: _____

**THE USE OF LIPOSOMAL BUPIVACAINE FOR PAIN CONTROL FOLLOWING
MASTECTOMY AND IMMEDIATE IMPLANT BASED BREAST
RECONSTRUCTION**

Wake Forest Baptist Comprehensive Cancer Center
CCCWFU # 99517

Appendix D – Mandatory STRC SAE Reporting Guidelines

Safety and Toxicity Review Committee (STRC; previously known as CROC) Serious Adverse Event (SAE) Notification SOP	Date: 8/17/2016
---	------------------------

Mandatory STRC SAE Reporting Requirements

This document describes STRC reporting and use of the electronic submission form that is submitted for **unexpected grade 4 and any grade 5 (death during protocol intervention)** SAEs on WFBCCC Institutional interventional trial patients. There are multiple entities that require reporting of SAEs. Each entity has different rules for what is reported, and how it is reported.

Rules used by other entities (Institutional Review Board (IRB), AdEERS, MedWatch, etc.) should NOT be used to evaluate whether an event should be reported to STRC. Only the rules for reporting described in this document should be considered.

As defined in the NCI Data Table 4 reporting guidelines, **WFBCCC Institutional Interventional studies covered by these reporting requirements are defined as: In-house, internally reviewed trials, including those collaborative studies conducted with industry sponsorship in which the center is a primary contributor to the design, implementation, and monitoring of the trial, or participation in a multi-site trial initiated by an institutional investigator at another center.** Institutional trials are almost always authored by a researcher here at WFBCCC. Institutional protocols are labeled NCI Code="I" for Institutional on the protocol screen in ORIS. Cooperative group protocols are **not** considered Institutional, but Research Base trials **are** classified as Institutional.

The STRC is responsible for reviewing SAEs for WFBCCC Institutional Interventional studies, as defined above. STRC currently requires that unexpected grade 4 and all grade 5 SAEs on these trials be reported to the STRC for review. All Clinical Protocol and Data Management (CPDM) staff members assisting a PI in documenting and reporting an SAE that qualifies for STRC reporting are responsible for informing a clinical member of the STRC by phone (or in-person), followed by informing the entire committee via the required email notification.

THESE REPORTING REQUIREMENTS APPLY TO any faculty or staff member on the study team for a WFBCCC Institutional Interventional trial. Once an event is observed, it is the responsibility of the person who observed the event to be sure that it is reported.

What is considered an SAE under this mandatory procedure?

Any **unexpected grade 4** event and **all grade 5 events** (death during protocol intervention) should be reported. These events should be reported if they occur while a patient is on study

THE USE OF LIPOSOMAL BUPIVACAINE FOR PAIN CONTROL FOLLOWING
MASTECTOMY AND IMMEDIATE IMPLANT BASED BREAST
RECONSTRUCTION

Wake Forest Baptist Comprehensive Cancer Center
CCCWFU # 99517

treatment or if they occur within 30 days of last study treatment (even if patient begins a new treatment during the 30 days). This window of 30 days should be the standard window to be used in all protocols unless a specific scientific rationale is presented to suggest that a shorter window

	ADVERSE EVENT					
	Grade 1, Grade 2, Grade 3		Grade 4		Grade 5	
	Unexpected	Expected	Unexpected	Expected	Unexpected	Expected
Unrelated	Not Required	Not Required	REPORT TO STRC	Not Required	REPORT TO STRC	REPORT TO STRC
Unlikely	Not Required	Not Required	REPORT TO STRC	Not Required	REPORT TO STRC	REPORT TO STRC
Possible	Not Required	Not Required	REPORT TO STRC	Not Required	REPORT TO STRC	REPORT TO STRC

can be used to identify events. In addition, if it is not clear whether the Grade 4 is unexpected it should be reported.

Table 1: Summary of STRC Reporting Requirements for Institutional Pilot, Phase 1, Phase 2 and Phase 3 Interventional Trials

STRC reporting may not be appropriate for specific expected adverse events for protocols. In those situations the adverse events that will not require STRC reporting **must be specified in the text of the approved protocol.**

**THE USE OF LIPOSOMAL BUPIVACAINE FOR PAIN CONTROL FOLLOWING
MASTECTOMY AND IMMEDIATE IMPLANT BASED BREAST
RECONSTRUCTION**

Wake Forest Baptist Comprehensive Cancer Center
CCCWFU # 99517

Probable	Not Required	Not Required	REPORT TO STRC	Not Required	REPORT TO STRC	REPORT TO STRC
Definite	Not Required	Not Required	REPORT TO STRC	Not Required	REPORT TO STRC	REPORT TO STRC

STRC notification responsibilities of the person handling the reporting/documenting of the SAE:

1. Make a phone call (or speak in person) to the appropriate clinical member of the STRC as listed below (page if necessary)—see note 2 below
2. Submit the STRC Notification Form WITHIN 24 HOURS of first knowledge of the event. This form is found at either the ORIS main menu page or by going to <http://ccc.wfubmc.edu/oris/strc.aspx>. This will ensure that all persons that need to be made aware of the event (i.e., study team members and STRC members) will be notified; remember to file a copy of your confirmation. (Form instructions will walk you through the required fields, consult the help page for further instructions.)
3. Ensure that you document that the appropriate person(s) on the STRC has been contacted. This documentation is placed on the STRC Notification form described above.
4. Follow up with/update the clinical member(s) of STRC regarding any new developments or information obtained during the course of the SAE investigation and reporting process.

Elements to complete the electronic STRC form:

Please use 'reply to All' when responding with one of these terms: Definite, Probable, Possible, Unlikely, or Unrelated

1. Patient ID (ORIS PID)
2. Patient Name
3. Patient MR#
4. WFBCCC(ORIS) Study Number
5. Title
6. PI Name
7. PI Contact Number
8. PI Comments
9. STRC Clinician notified by Phone
10. Notified Date
11. Notified Time
12. STRC Clinician Comments
13. Category [This is the Grade – Either Unexpected Grade 4 or Grade 5 should be entered]
14. Additional Information (IRB Reporting)(after discussion with PI or STRC Clinician)
 - i. Is This Event Related to Protocol Treatment?

**THE USE OF LIPOSOMAL BUPIVACAINE FOR PAIN CONTROL FOLLOWING
MASTECTOMY AND IMMEDIATE IMPLANT BASED BREAST
RECONSTRUCTION**

Wake Forest Baptist Comprehensive Cancer Center
CCCWFU # 99517

- ii. Is Suspension of the Protocol Needed?
- iii. Any Changes to Consent or Protocol Needed?
- iv. Was Nature or Severity of Event Unexpected?

15. Date of the event.
16. Brief description (include brief clinical history relevant to this event, including therapies believed related to event).
17. Date of Last Dose before event
18. Relevant tests/labs.
19. Other Relevant Treatment Information
20. Other Comments/Notes (include regimen of chemo and dates the patient received them if known).
21. Cc (email) (include treating Physician; separate email list with comma",")
22. Your Name
23. Your Email
24. Confirm Your Email

The Clinical Members of STRC to Notify by Phone or Page:

[name] – Director-at-Large, WFBCCC; Chair, PRC; Section Head, Hematology/Oncology. [name] / [contact]

